**Nivolumab administration should be delayed for the following:**

Any Grade  $\geq 2$  non-skin, drug-related AE, with the following exceptions:

- Grade 2 drug-related fatigue or laboratory abnormalities do not require a treatment delay
- Any Grade 3 skin, drug-related AE

Any Grade 3 drug-related laboratory abnormality, with the following exceptions for lymphopenia, leukopenia, AST, ALT, total bilirubin, or asymptomatic amylase or lipase:

- Grade 3 lymphocyte count decreased or white blood cell decreased does not require dose delay.
- If a subject has a baseline AST, ALT, or total bilirubin that is within normal limits, delay dosing for drug-related Grade  $\geq 2$  toxicity.
- If a subject has baseline AST, ALT, or total bilirubin within the Grade 1 toxicity range, delay dosing for drug-related Grade  $\geq 3$  toxicity.
- Any Grade  $\geq 3$  drug-related amylase or lipase abnormality that is not associated with symptoms or clinical manifestations of pancreatitis does not require dose delay. The Investigator should be consulted for such Grade  $\geq 3$  amylase or lipase abnormalities.

Any AE, laboratory abnormality, or intercurrent illness that, in the judgment of the investigator, warrants delaying the dose of study medication.

**4.3.2.2 Criteria to Resume Nivolumab Treatment**

Subjects may resume treatment with study drug when the drug-related AE(s) resolve to Grade  $\leq 1$  or baseline value, with the following exceptions:

- Subjects may resume treatment in the presence of Grade 2 fatigue
- Subjects who have not experienced a Grade 3 drug-related skin AE may resume treatment in the presence of Grade 2 skin toxicity
- Subjects with baseline Grade 1 AST/ALT or total bilirubin who require dose delays for reasons other than a 2-grade shift in AST/ALT or total bilirubin may resume treatment in the presence of Grade 2 AST/ALT OR total bilirubin
- Subjects with combined Grade 2 AST/ALT AND total bilirubin values meeting discontinuation parameters should have treatment permanently discontinued
- Drug-related pulmonary toxicity, diarrhea, or colitis, must have resolved to baseline before treatment is resumed. Subjects with persistent Grade 1 pneumonitis after completion of a steroid taper over at least 1 month may be eligible for retreatment if investigator allows.
- Subjects with drug-related endocrinopathies adequately controlled with only physiologic hormone replacement may resume treatment if the investigator allows it, but this should be documented clearly in the electronic case report form (eCRF).

If the criteria to resume treatment are met, the subject should restart treatment at the next scheduled time point per protocol. However, if the treatment is delayed past the next scheduled time point per protocol, the next scheduled time point will be delayed until dosing resumes.

If treatment is delayed or interrupted for > 6 weeks, the subject must be permanently discontinued from study therapy, except as specified in the discontinuation section.

#### 4.3.2.3 Management Algorithms for Nivolumab

Guidelines for the management of immune-related events can be found in the approved United States Product insert.

Immuno-oncology (I-O) agents are associated with AEs that can differ in severity and duration than AEs caused by other therapeutic classes. Nivolumab is considered an I-O agent in this protocol. Early recognition and management of AEs associated with immuno-oncology agents may mitigate severe toxicity.

Management algorithms (See [Appendix C](#), section 11.3) have been developed to assist investigators in assessing and managing the following groups of AEs:

- Gastrointestinal,
- Renal,
- Pulmonary,
- Hepatic,
- Endocrinopathies,
- Skin, and
- Neurological.

For subjects expected to require more than 4 weeks of corticosteroids or other immunosuppressants to manage an AE, consider recommendations provided in the algorithms. These algorithms are found in the Nivolumab IB and in [Appendix C](#), section 11.3 of this protocol. The guidance provided in these algorithms should not replace the Investigator's medical judgment but should complement it.

#### 4.3.2.4 Discontinuation Criteria for Nivolumab

Treatment should be permanently discontinued for the following:

- Any Grade 2 drug-related uveitis or eye pain or blurred vision that does not respond to topical therapy and does not improve to Grade 1 severity within the re-treatment period OR requires systemic treatment
- Any Grade 3 non-skin, drug-related adverse event lasting > 7 days, with the following exceptions:
  - Grade 3 drug-related uveitis, pneumonitis, bronchospasm, hypersensitivity reaction, or infusion reaction of any duration requires discontinuation

- Grade 3 drug-related endocrinopathies adequately controlled with only physiologic hormone replacement do not require discontinuation
- Grade 3 drug-related laboratory abnormalities do not require treatment discontinuation except those noted below
- Grade 3 drug-related platelet count decreased > 7 days or associated with bleeding requires discontinuation
- Any drug-related hepatic abnormality that meets the following criteria require discontinuation:
  - AST or ALT > 8 x ULN
  - Total bilirubin > 5 x ULN
  - Concurrent AST or ALT > 3 x ULN and total bilirubin > 2 x ULN
- Any Grade 4 drug-related adverse event or laboratory abnormality, except for the following events which do not require discontinuation:
  - Isolated Grade 4 amylase or lipase abnormalities that are not associated with symptoms or clinical manifestations of pancreatitis and decrease to < Grade 4 within 1 week of onset.
  - Isolated Grade 4 electrolyte imbalances/abnormalities that are not associated with clinical sequelae and are corrected with supplementation/appropriate management within 72 hours of their onset
  - Grade 4 lymphocyte count decreased or white blood cell decreased
  - Grade 4 drug-related endocrinopathy adverse events, such as adrenal insufficiency, ACTH deficiency, hyper- or hypothyroidism, or glucose intolerance, which resolve or are adequately controlled with physiologic hormone replacement (corticosteroids, thyroid hormones) or glucose-controlling agents, respectively, may not require discontinuation after discussion with and approval from the Investigator
- Any dosing interruption lasting > 6 weeks with the following exceptions:
  - Dosing delays or interruptions to allow for prolonged steroid tapers to manage drug-related adverse events are allowed. Prior to re-initiating treatment in a subject with a dosing interruption lasting > 6 weeks, the Investigator must be consulted. Tumor assessments should continue as per protocol even if dosing is interrupted or delayed
  - Dosing interruptions or delays lasting > 6 weeks that occur for non-drug-related reasons may be allowed if approved by the Investigator. Prior to re-initiating treatment in a subject with a dosing interruption lasting > 6 weeks, the Investigator must be consulted. Tumor assessments should continue as per protocol even if dosing is interrupted
- Permanently discontinue nivolumab for grade 3 myocarditis

- Any adverse event, laboratory abnormality, or intercurrent illness which, in the judgment of the Investigator, presents a substantial clinical risk to the subject with continued nivolumab dosing

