#### 4.3.2 Nivolumab Dose Modifications/Delays

Toxicity grades per NCI-CTCAE Criteria v5.0

Adverse Reaction	Severity	Dose Modification
Colitis	Grade 2 diarrhea or colitis	Withhold dose a
	Grade 3 diarrhea or colitis	Withhold dose a when administered as a single agent
		Permanently discontinue when administered with ipilimumab
	Grade 4 diarrhea or colitis	Permanently discontinue
Pneumonitis	Grade 2 pneumonitis	Withhold dose a
	Grade 3 or 4 pneumonitis	Permanently discontinue
Hepatitis/non-HCC b	Aspartate aminotransferase (AST)/ or alanine aminotransferase (ALT) more than 3 and up to 5 X the ULN or total bilirubin $> 1.5$ and up to 3X ULN	Withhold dose a
	AST or ALT more than 5X ULN or total bilirubin $> 3X$ ULN	Permanently discontinue
Hepatitis/HCC b	If AST/SLT is within normal limits at baseline and increases to more than 3 and up to 5 times the ULN or total bilirubin more than 1.5 and up to 3 times the ULN	Withhold dose c
	If AST/ALT is more than 1 and up to 3	

	times ULN at baseline and increases to more than 5 and up to 10 times the ULN  If AST/ALT is more than 3 and up to 5 times ULN at baseline and increases to more than 8 and up to 10 times ULN	
	If AST/ALT is more than 3 and up to 5 times ULN at baseline and increases to more than 8 and up to 10 times the ULN	Permanently discontinue
Hypophysitis	Grade 2 or 3 hypophysitis	Withhold dose a
	Grade 4 hypophysitis	Permanently discontinue
Adrenal insufficiency	Grade 2 adrenal insufficiency	Withhold dose a
	Grade 3 or 4 adrenal insufficiency	Permanently discontinue
Type 1 Diabetes Mellitus	Grade 3 hyperglycemia	Withhold dose a
	Grade 4 hyperglycemia	Permanently discontinue
Nephritis and Renal Dysfunction	Serum creatinine more than 1.5 and up to 6X ULN	Withhold dose a
	Serum creatinine more than 6X ULN	Permanently discontinue
Skin	Grade 3 rash or suspected Stevens-Johnson syndrome (SJS) or toxic epidermal necrolysis (TEN)	Withhold dose a
	Grade 4 rash or confirmed SJS or TEN	Permanently discontinue
Encephalitis	New-onset moderate or severe neurologic signs or symptoms	Withhold dose a
	Immune-mediated encephalitis	Permanently discontinue
Other	Other Grade 3 adverse reaction First occurrence	Withhold dose a
	Recurrence of same Grade 3 adverse reaction	Permanently discontinue
	Life-threatening or Grade 4 adverse reaction	Permanently discontinue

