	Grade 3 myocarditis	Permanently discontinue
	Requirement for 10 mg per day or greater prednisone or equivalent for more than 12 weeks	Permanently discontinue
	Persistent Grade 2 or 3 adverse reactions lasting 12 weeks or longer	Permanently discontinue

- a) Resume treatment when adverse reaction returns to Grade 0 or 1.
- b) HCC: hepatocellular carcinoma
- c) Resume treatment when AST/ALT returns to baseline.

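### For a first *Other* Grade 3 event that lasts more than 7 days and then recovers, the nivolumab table leads to restarting treatment while section 4.3.2.4 stops it permanently, and no text says which governs

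*Combined protocol and SAP*

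**What the plan says.** Three parts of the protocol govern nivolumab after a Grade 3 event.

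- **Section 4.3.2, table.** The row "Other Grade 3 adverse reaction First occurrence" carries the action withhold, with footnote a: "Resume treatment when adverse reaction returns to Grade 0 or 1". Recurrence of the same Grade 3 reaction means permanent discontinuation. So does a Grade 2 or 3 reaction that persists for 12 weeks or more.
- **Section 4.3.2.2.** "Subjects may resume treatment with study drug when the drug-related AE(s) resolve to Grade" 1 or lower, or to baseline, subject to listed exceptions. Subjects who meet the criteria should then restart at the next scheduled time point.
- **Section 4.3.2.4.** Treatment should be permanently discontinued for "Any Grade 3 non-skin, drug-related adverse event lasting > 7 days, with the following exceptions". The exceptions remove most laboratory abnormalities and hormone-controlled endocrinopathies from the 7-day rule. They make uveitis, pneumonitis, bronchospasm, hypersensitivity and infusion reactions a stop at any duration.

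Section 4.3.2.2 lets discontinuation control in two places only. One is the bullet on combined Grade 2 AST/ALT and bilirubin values. The other is the sentence on interruptions longer than 6 weeks, which refers to the discontinuation section.

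**The concern.** The table gives an instruction to resume with no condition on how long the Grade 3 phase lasted, beyond the 12-week persistence row. Section 4.3.2.4 puts a limit of 7 days on that phase. A clinician working from the table would rechallenge a patient whom 4.3.2.4 says must not receive nivolumab again. Section 9.5 requires the study to be conducted exactly as described in the protocol, and here following one section means departing from another. At stake is the consistency of a safety decision in individual patients at Dose Level 2 and in Phase II.

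**Working it through.** No statistical figure is involved, so the check is a comparison of the texts.

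**1. Events in scope.** The event must be Grade 3, drug-related, non-skin, clinical rather than laboratory, a first occurrence, not named in another table row, and not among the 4.3.2.4 exceptions. Many Grade 3 events fall outside this. For pneumonitis, for example, the table and 4.3.2.4 both require a permanent stop.

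**2. Worked case.** Assume that such an event lasts 10 days at Grade 3 and then returns to baseline. The 10 days are an illustration, not a figure from the protocol.

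| Source | Instruction |
|---|---|
| Table, *Other* row and footnote a | Withhold, then resume at Grade 0 or 1 |
| 4.3.2.2 | May resume; should restart at the next scheduled time point |
| 4.3.2.4 | Stop permanently, because 10 > 7 days |

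**3. Range of disagreement.** The table's persistence limit is 12 × 7 = 84 days. By event duration, the table and 4.3.2.4 therefore disagree from more than 7 days up to 84 days. The separate rule on interruptions longer than 6 weeks (6 × 7 = 42 days), which has its own exceptions, may end treatment sooner.

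**4. Is one source always the stricter?** If it were, a reader could infer which governs. It is not.

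- *4.3.2.4 is stricter* for the 7-day rule. It is also stricter for Grade 3 uveitis, bronchospasm and hypersensitivity, which it stops at any duration while the *Other* row withholds. Concurrent AST/ALT > 3x ULN with bilirubin > 2x ULN is a stop in 4.3.2.4 but a withhold within the table's bands of 3–5x and 1.5–3x. A Grade 3 platelet decrease that lasts more than 7 days or comes with bleeding is a stop in 4.3.2.4 and a first-occurrence withhold in the table.
- *The table is stricter* for liver tests outside hepatocellular carcinoma: "AST or ALT more than 5X ULN or total bilirubin" > 3x ULN is a stop, against "AST or ALT > 8 x ULN" and bilirubin > 5x ULN in 4.3.2.4. The readable footnote to the hepatic algorithm in Appendix C allows delay up to 8x and 5x. The table also stops for Grade 3 adrenal insufficiency, while 4.3.2.4 does not require a stop if the condition is controlled on physiologic hormone replacement.

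**5. Does the one clause cover the first group?** Yes. Footnote a and the 4.3.2.2 opening sentence are the routes back to treatment for these events. Making both conditional on 4.3.2.4 settles every case in which 4.3.2.4 is the stricter text. It leaves the second group, which needs its own decision.

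**The case against.** The strongest reply is that the sections form a sequence of delay, resume and discontinue. Withholding is the action at onset, when duration is unknown; the 7-day criterion can be met only later, and a permanently discontinued patient is no longer a candidate to resume. Section 4.3.2.2 says subjects *may* resume, while 4.3.2.4 says treatment *should* stop. This reading is plausible and probably intended, so 4.3.2.2 is the weaker half of the conflict. But the table is not only a list of delays: it has its own permanent-stop rows, including one on duration, and footnote a contains no pointer to 4.3.2.4. Where the authors wanted discontinuation to control resumption they said so, and this event is not one of those places.

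A reader might take Grade 3 colitis as the natural example. The table does say "Permanently discontinue when administered with ipilimumab", and 4.3.2.2 adds "Drug-related pulmonary toxicity, diarrhea, or colitis, must have resolved to baseline before treatment is resumed". But the withhold instruction for Grade 3 colitis is limited to single-agent use. Nivolumab is given here with talimogene laherparepvec, so the row does not cleanly apply during combination cycles. The gastrointestinal flowchart in Appendix C could not be read in the copy reviewed. The conflict should rest on the *Other* row.

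It can also be said that the principal investigator oversees every patient's treatment (section 9.8) and may stop nivolumab for any substantial clinical risk (section 4.3.2.4). That limits the practical harm, but it only adds grounds for stopping. It does not say which instruction applies.

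**Conclusion.** The point holds and is minor. For the events defined in step 1 of the check, the text is wrong as written: the table leads to restarting nivolumab and 4.3.2.4 requires a permanent stop. The documents give no rate for such events, so the number of patients affected cannot be stated. Sample size, alpha and power are unaffected.

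Two stronger readings are not supported. A reader might infer that the rules conflict for every prolonged Grade 3 event; the exceptions and the rows that already agree rule that out. A reader might also infer that the earlier stop should always win. Step 4 shows that neither source is consistently the stricter, and such a rule would cancel express exemptions in 4.3.2.4 (Grade 4 lymphocyte decrease, for example) and the bullet in 4.3.2.2 on controlled endocrinopathies.

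The conclusion rests on the readable text. The Appendix C flowcharts could not be checked, but section 4.3.2.3 describes them as a complement to investigator judgment and gives them no precedence over the other rules.

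**What to change.** Add to table footnote a and to the opening sentence of section 4.3.2.2: *unless 4.3.2.4 requires permanent discontinuation, in which case nivolumab is not resumed*.

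Do not add a general rule that the earlier stop applies. Instead, align these rows one by one, with the investigators choosing the limit for each:

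- AST/ALT, > 5x or > 8x ULN, and total bilirubin, > 3x or > 5x ULN. If the lower limits are chosen, the Appendix C hepatic footnote must change to match; if the higher, the table row changes.
- Grade 3 adrenal insufficiency controlled on hormone replacement: stop, or no stop required.

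The express exemptions in 4.3.2.4 are otherwise kept.

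The cost is a wording amendment. A few patients will stop nivolumab earlier than the table alone would allow, and would lose any benefit of further doses. No new data, visits or design change are needed.

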#### 4.3.3 Management of Nivolumab Infusion Reactions

Since nivolumab contains only human immunoglobulin protein sequences, it is unlikely to be immunogenic and induce infusion or hypersensitivity reactions. However, if such a reaction were to occur, it might manifest with fever, chills, rigors, headache, rash, pruritis, arthralgias, hypo- or hypertension, bronchospasm, or other symptoms of allergic-like reactions.

All Grade 3 or 4 infusion reactions should be reported as an SAE if criteria are met. Infusion reactions should be graded according to NCI CTCAEv5.0 guidelines.

Treatment recommendations are provided below and may be modified based on local treatment standards and guidelines as appropriate:

**For Grade 1 symptoms during nivolumab infusion:** (Mild reaction; infusion interruption not indicated; intervention not indicated). Remain at bedside and monitor subject until recovery from symptoms. The following prophylactic premedications are recommended for future infusions: diphenhydramine 50 mg (or equivalent) and/or paracetamol 325 to 1000 mg (acetaminophen) at least 30 minutes before additional nivolumab administrations.

**For Grade 2 symptoms during nivolumab infusion:** (Moderate reaction requires therapy or infusion interruption but responds promptly to symptomatic treatment [e.g., antihistamines, non-steroidal anti-inflammatory drugs, narcotics, corticosteroids, bronchodilators, IV fluids]; prophylactic medications indicated for 24 hours).

Stop the nivolumab infusion, begin an IV infusion of normal saline, and treat the subject with diphenhydramine 50 mg IV (or equivalent) and/or paracetamol 325 to 1000 mg (acetaminophen); remain at bedside and monitor subject until resolution of symptoms. Corticosteroid or bronchodilator therapy may also be administered as appropriate. If the infusion is interrupted, then restart the infusion at 50% of the original infusion rate when symptoms resolve; if no further complications ensue after 30 minutes, the rate may be increased to 100% of the original infusion rate. Monitor subject closely. If symptoms recur, then no further nivolumab will be administered at that visit. Administer diphenhydramine 50 mg IV, and remain at bedside and monitor the subject until resolution of symptoms. The amount of study drug infused must be recorded on the electronic case report form (eCRF). The following prophylactic premedications are recommended for future infusions: diphenhydramine 50 mg (or equivalent) and/or paracetamol 325 to 1000 mg (acetaminophen) should be administered at least 30 minutes before additional nivolumab administrations. If necessary, corticosteroids (recommended dose: up to 25 mg of IV hydrocortisone or equivalent) may be used.

**For Grade 3 or Grade 4 symptoms during nivolumab infusion:** (Severe reaction, Grade 3: prolonged [i.e., not rapidly responsive to symptomatic medication and/or brief interruption of infusion]; recurrence of symptoms following initial improvement; hospitalization indicated for other clinical sequelae [e.g., renal impairment, pulmonary infiltrates]). Grade 4: (life threatening; pressor or ventilatory support indicated).

Immediately discontinue infusion of the therapeutic antibody. Begin an IV infusion of normal saline, and treat the subject as follows. Recommend bronchodilators, epinephrine 0.2 to 1 mg of a 1:1000 solution for subcutaneous administration or 0.1 to 0.25 mg of a 1:10,000 solution injected slowly for IV administration, and/or diphenhydramine 50 mg IV with methylprednisolone 100 mg IV (or equivalent), as needed. Subject should be monitored until the investigator is comfortable that the symptoms will not recur. The offending therapeutic antibody will be permanently discontinued. Investigators should follow their institutional guidelines for the treatment of anaphylaxis. Remain at bedside and monitor subject until recovery from symptoms.

In the case of late-occurring hypersensitivity symptoms (e.g., appearance of a localized or generalized pruritis within 1 week after treatment), symptomatic treatment may be given (e.g., oral antihistamine, or corticosteroids).

#### **4.4 Concomitant Medications/Treatments**

Patients on the trial are allowed to receive all supportive care therapy needed to alleviate symptoms related to their cancer diagnosis or other medical problems at the investigator's discretion. No treatments should be withheld due to a patient's participation in this study. Prophylaxis for infusion-related reactions should be employed per institutional guidelines (also refer to Section 4.3.3).

Medications or vaccinations specifically prohibited in the exclusion criteria are not allowed during the ongoing trial. If there is a clinical indication for one of these or other medications or vaccinations specifically prohibited during the trial, discontinuation from trial therapy or vaccination may be required. The investigator should discuss any questions regarding this with the Bristol-Meyers-Squibb (BMS) Clinical team. The final decision on any supportive therapy or vaccination rests with the investigator and/or the subject's primary physician.

##### **4.4.1 Special warnings and precautions**

- Nivolumab is associated with immune-related AEs. Subjects should be monitored continuously as an AE with nivolumab may occur at any time during or after discontinuation of therapy.

- For suspected immune-related reactions, adequate evaluation should be performed to confirm etiology or exclude other causes. Based on the severity of the adverse reaction, nivolumab should be withheld and corticosteroids administered. If immunosuppression with corticosteroids is used to treat an AE, a taper of at least 1-month duration should be initiated upon improvement. Rapid tapering may lead to worsening of the AE. Non-corticosteroid immunosuppressive therapy should be added if there is worsening or no improvement despite corticosteroid use.

